### 6.13.3.10.2. Suicidal Ideation and Behavior Solicited Through C-SSRS

Suicide-related thoughts and behaviors occurring during the entire study period, based on the C-SSRS, will be summarized by treatment group. In particular, for each of the following suicide-related events, the counts and percentages of participants with the event will be summarized by treatment group:

- died by suicide
- nonfatal suicide attempt
- interrupted attempt
- aborted attempt
- preparatory acts or behavior
- active suicidal ideation with specific plan and intent
- active suicidal ideation with some intent to act without specific plan
- active suicidal ideation with any methods (no plan) without intent to act

- nonspecific active suicidal thoughts
- wish to be dead, and
- non-suicidal, self-injurious behavior.

In addition, the counts and percentages of participants who experienced at least 1 of the composite measures will be presented. The participants with at least 1 post-baseline C-SSRS assessment are included. The composite measure is determined at each assessment by the "yes" or "no" responses in C-SSRS categories by the study participant:

- Category 1 Wish to be Dead
- Category 2 Non-specific Active Suicidal Thoughts
- Category 3 Active Suicidal Ideation with Any Methods (Not Plan) without Intent to Act
- Category 4 Active Suicidal Ideation with Some Intent to Act, without Specific Plan
- Category 5 Active Suicidal Ideation with Specific Plan and Intent
- Category 6 Preparatory Acts or Behavior
- Category 7 Aborted Attempt
- Category 8 Interrupted Attempt
- Category 9 Actual Attempt (non-fatal), and
- Category 10 Completed Suicide.

Composite endpoints of suicidal ideation and suicidal behavior based on the above categories are defined below:

- Suicidal ideation: A "yes" answer at any time during study to any 1 of the 5 suicidal ideation questions (Categories 1 through 5) on the C-SSRS.
- Suicidal behavior: A "yes" answer at any time during study to any 1 of the 5 suicidal behavior questions (Categories 6 through 10) on the C-SSRS.
- Suicidal ideation or behavior: A "yes" answer at any time during study to any 1 of the 10 suicidal ideation and behavior questions (Categories 1 through 10) on the C-SSRS.

A listing contains data for each participant with suicidal ideation, suicidal behavior, or non-suicidal self-injurious behavior during the study by treatment and visit. Data from all visits are displayed, regardless of a "yes" or "no" answer, for patients with any "yes" answer for suicidal ideation, suicidal behavior, or self-injurious behavior without suicidal intent.

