Note: Participants with MDD or generalized anxiety disorder whose disease state is considered stable and expected to remain stable throughout the course of the study, in the opinion of the investigator, may be considered for inclusion if they are not on excluded medications

- 17. Have any lifetime history of a suicidal attempt
- 18. Have a PHQ-9 score of 15 or more at Visit 1 or 2, prior to randomization.
- 19. On the C-SSRS at Visits 1 or 2, prior to randomization:
 - o answered "yes" to Question 4 or Question 5 on the "Suicidal Ideation" portion of the C-SSRS, or
 - o answered "yes" to any of the suicide-related behaviors on the Suicidal Behavior portion of the C-SSRS.

and

- o the ideation or behavior occurred within the past month
- 20. Have uncontrolled hypertension (systolic blood pressure above or equal to 160 mmHg and/or diastolic blood pressure above or equal to 100 mmHg)
- 21. Have any of the following cardiovascular conditions within 3 months prior to randomization: acute myocardial infarction, cerebrovascular accident (stroke), unstable angina, or hospitalization due to congestive heart failure (CHF)
- 22. Have NYHA Functional Classification IV CHF
- 23. Have acute or chronic hepatitis, signs and symptoms of any other liver disease other than nonalcoholic fatty liver disease, or any of the following, as determined by the central laboratory during screening:
 - Alanine aminotransferase (ALT) level >3.0x the upper limit of normal (ULN) for the reference range

or

o Alkaline phosphatase (ALP) level >1.5x the ULN for the reference range

or

Total bilirubin (TBL) level >1.2x the ULN for the reference range (except for cases of known Gilbert's Syndrome)

Note: Participants with nonalcoholic fatty liver disease (NAFLD) are eligible to participate in this trial if their ALT level is \leq 3.0x ULN for the reference range.

- 24. Have a calcitonin level (at Visit 1) of:
 - \circ \geq 20 ng/L at Visit 1, if eGFR \geq 60 mL/min/1.73 m²
 - \circ \geq 35 ng/L at Visit 1, if eGFR <60 mL/min/1.73 m²

- 25. Have a family or personal history of medullary thyroid carcinoma (MTC) or Multiple Endocrine Neoplasia (MEN) syndrome type 2
- 26. Have a history of an active or untreated malignancy or are in remission from a clinically significant malignancy (other than basal or squamous cell skin cancer, in situ carcinomas of the cervix, or in situ prostate cancer) for less than 5 years

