9.2.2. Adverse Event Monitoring with a Systematic Questionnaire

Patients with overweight and obesity are at increased risk for depression (Luppino et al. 2010). Depression can increase the risk for suicidal ideation and behavior. Therefore, study participants will be screened at trial entry and monitored during the study for depression, suicidal ideation and behavior.

Baseline and treatment-emergent assessment of depression, suicidal ideation and behavior will be monitored during the study using the C-SSRS and PHQ-9 (Section 9.4.6).

The C-SSRS is a scale that captures the occurrence, severity, and frequency of suicidal ideation and/or behavior during the assessment period. The scale includes suggested questions to solicit the type of information needed to determine if suicidal ideation and/or behavior occurred. The tool was developed by the National Institute of Mental Health trial group for the purpose of being a counterpart to the Columbia Classification Algorithm of Suicide Assessment categorization of suicidal events.

The PHQ-9 is a validated self-report screening tool that assesses the presence and intensity of depressive symptoms. The PHQ-9, which incorporates the 9 Diagnostic and Statistical Manual-IV depression criteria "0" (not at all) to "3" (nearly every day), was developed for use in primary care settings (Kroenke et al. 2001).

Nonserious AEs obtained through the questionnaire are recorded and analyzed separately. Only *serious* AEs elicited through the C-SSRS or PHQ-9 are to be recorded as AEs via the eCRF and reported to Lilly or its designee within 24 hours as SAEs. For this study, the C-SSRS is adapted for the assessment of the ideation and behavior categories only. The Intensity of Ideation and Lethality of Behavior sections are removed.

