## 6.13. Safety Analyses

Unless specified otherwise, safety assessments will be based on the SS (Table GPIA.6.1). All events that occur between the first dose date of study drug and the end date of study participation will be included, regardless of the adherence to study drug.

The statistical assessment of homogeneity of the distribution of categorical safety responses between tirzepatide doses and placebo will be conducted using Fisher's exact test, unless specified otherwise.

For the selected continuous safety parameters, the mean change from baseline differences vs. placebo will be assessed via an MMRM using REML. Data from scheduled visits will be utilized for this analysis unless specified otherwise, the model for the analysis during 52 weeks treatment period will include sex, presence of comorbidities at randomization, treatment group, visit and treatment-by-visit interaction as fixed effects, and baseline value of the safety parameter as a covariate. To model the covariance structure within participants, the unstructured covariance matrix will be used. If this model fails to converge, the covariance structures specified in Section 6.12.1.1 will be tested in order until met convergence. If the data does not warrant the MMRM model, then ANCOVA model will be conducted.

For selected safety parameters, time-to-first-event analysis via the Cox-proportional hazards model may be conducted. Participants without the event will be censored at the end of study participation. For participants experiencing the event, the "time-to-first-event" will be the time (in days) from first dose to first occurrence of the event.

Where necessary, the rate of events will be analyzed using a generalized linear mixed-effects model assuming the number of events follow a negative binomial distribution and with treatment as a fixed effect. The logarithm of days during the active treatment period will be adjusted as an offset to account for possible unequal treatment duration of follow-up between participants.

Unless otherwise specified, all the analyses listed in this section will be conducted using SS in the postbaseline period: up to 52 weeks treatment period plus the safety follow-up (Visit 801, if applicable) for all randomized participants.

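### The C-SSRS counts in SAP 6.13.3.10.2 are not limited to answers given after the first dose and are not compared with baseline, which on its face conflicts with the safety window in SAP 6.13

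*SAP*

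**What the plan says.** **C-SSRS section (SAP 6.13.3.10.2).** The item-level summary reads: "Suicide-related thoughts and behaviors occurring during the entire study period, based on the C-SSRS, will be summarized by treatment group". The ideation composite is a yes "answer at any time during study to any 1 of the 5 suicidal ideation questions (Categories 1 through 5) on the C-SSRS"; the behaviour composite is built the same way from Categories 6 to 10. The combined composite is a yes "answer at any time during study to any 1 of the 10 suicidal ideation and behavior questions". On who is counted, the section says: "The participants with at least 1 post-baseline C-SSRS assessment are included". It gives no start date for the answers and no comparison with baseline.

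**General safety rule (SAP 6.13).** Unless otherwise specified, "all the analyses listed in this section will be conducted using SS in the postbaseline period", running through Visit 801. The same section takes the first dose as the start for events.

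**Safety Analysis Set.** SAP Table GPIA.6.1 limits the set to data from the treatment and follow-up periods. Protocol Table GPIA.4 gives it the whole study.

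**Protocol on the C-SSRS.** Section 9.2.2 says: "Baseline and treatment-emergent assessment of depression, suicidal ideation and behavior will be monitored during the study using the C-SSRS and PHQ-9". The analysis in Section 10.3.4.4.3 is a listing by participant and visit, with details left to the SAP.

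**The concern.** The composite rule turns on whether a yes was given during the study, and the answers at Visits 1 and 2 are given during the study. Both visits come before treatment, because the first dose is taken at the end of Visit 2. Two programmers working from this text could produce different tables.

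The table matters because protocol 9.2.2 records only serious events elicited by the C-SSRS or PHQ-9 as adverse events. Nonserious C-SSRS findings appear between arms only here, apart from an optional COVID-19 breakdown of the same data in SAP 8.6. If pre-dose answers enter, the percentages no longer describe what happened on treatment, and any ratio between arms is pulled towards 1.

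A second gap remains even on the favourable reading. Someone with the same passive ideation before and after dosing counts as an event, and nothing shows whether a participant became worse. The PHQ-9 section just above (SAP 6.13.3.10.1) handles this with baseline-to-postbaseline shift tables and counts of worsening.

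**Working it through.** The documents state no C-SSRS rate, expected count or power, so there is no figure to reproduce. The check is first textual, then illustrative.

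**1. Can a pre-dose yes exist in an eligible participant?** Yes.
- The Schedule of Activities places the Baseline/Screening version at Visit 1 and the Since Last Visit version from Visit 2 onward.
- Exclusion 19 covers Question 4 or 5 ideation, or suicidal behaviour, and only if "the ideation or behavior occurred within the past month". Categories 1 to 3 are not excluded.
- Exclusion 17 removes anyone with a lifetime attempt.
- What remains is mainly Categories 1 to 3, plus Question 4 or 5 ideation and non-attempt behaviour more than a month old.

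**2. Does the SAP keep those answers out?** The texts point in different directions.

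| Text | Points to |
|---|---|
| 6.13.3.10.2, item and composite rules | any visit, read literally |
| 6.13.3.10.2, inclusion rule | restricts participants, not answers |
| 6.13, default window | postbaseline, unless otherwise specified |
| SAP Table GPIA.6.1 | treatment plus follow-up |
| Protocol Table GPIA.4 | whole study |
| 6.13.3.4.2 and 6.13.5, similar phrase | adding follow-up, and saying so |
| Table GPIA.6.2, baseline definitions | silent on questionnaires |

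The SAP does not say whether the C-SSRS wording counts as a different specification for the purpose of the default.

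**3. What would the literal reading do?** Let b be the share with a pre-dose yes, equal in expectation across arms by randomisation. Let q be the postbaseline risk, assumed independent of b.

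- Any-time risk = b + (1 − b)q
- Any-time risk difference = (1 − b)(q_tirzepatide − q_placebo)

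Example with b = 5%, q = 2% on placebo and 6% on pooled tirzepatide:

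- placebo: 0.05 + 0.95 × 0.02 = 6.9%
- tirzepatide: 0.05 + 0.95 × 0.06 = 10.7%
- ratio: 10.7 / 6.9 = 1.55, against 6 / 2 = 3.0
- difference: 3.8 points, against 4.0

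Fisher power below is exact, two-sided 0.05, with 140 pooled tirzepatide participants against 70 on placebo.

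| b | Ratio | Difference (points) | Power |
|---|---|---|---|
| 0 | 3.00 | 4.00 | 14% |
| 1% | 2.33 | 3.96 | 13% |
| 2% | 1.99 | 3.92 | 12% |
| 5% | 1.55 | 3.80 | 10% |
| 10% | 1.31 | 3.60 | 8% |

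Two other assumed cases, each with b going from 0 to 5%, show how far the answer depends on the assumptions:

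- **10% against 1%:** the ratio falls from 10 to 2.4, the difference from 9.0 to 8.55 points, and power from 74% to 41%.
- **4% against 1%:** the ratio falls from 4.0 to 1.5 and the difference from 3.0 to 2.85 points. Power is 5.6% before and 7.0% after, so none is lost.

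**The case against.** The case for a postbaseline reading is strong. The SAP's own Safety Analysis Set holds no screening data. The default in 6.13 starts at the first dose. In the liver and ECG sections, wording about the whole study serves to bring in off-drug follow-up, and the C-SSRS section can be read the same way. The item-level rule speaks of thoughts and behaviours that occur during the study, which history recalled at Visit 1 is not. All of this stands, and it makes the defect one of ambiguity. It does not remove it: 6.13 already includes Visit 801, the C-SSRS section carries no follow-up qualifier, and the composites depend on when the answer is given.

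A reader might infer three stronger claims. The documents do not support them.

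- **That the plan definitely reports pre-treatment ideation as a trial event and hides a drug signal.** The plan does not settle inclusion, and the size rests on a pre-dose rate that nobody has stated.
- **That the protocol requires treatment-emergent C-SSRS counts.** Section 9.2.2 describes monitoring, and the only C-SSRS analysis that the protocol specifies is a listing.
- **That the adverse event of special interest is distorted.** SAP 6.13.3.10 builds it from treatment-emergent adverse event terms.

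The section also promises counts and percentages without naming a test of its own. The Fisher default in 6.13 compares tirzepatide doses with placebo, so for one dose arm (70 against 70) power in the 10% against 1% case is 52% even with no pre-dose answers. Finally, the planned listing shows every visit for anyone with a yes, so pre-dose answers can be traced; that does not correct the summary percentages.

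**Conclusion.** The point holds as an ambiguity with an apparent internal conflict. SAP 6.13.3.10.2 does not restrict C-SSRS answers to the postbaseline period and makes no baseline comparison, while SAP 6.13 and the SAP's Safety Analysis Set imply postbaseline data and the protocol's Safety Analysis Set does not.

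Under the literal reading, percentages would be expected to rise in all arms and ratios would shrink. In the 6% against 2% illustration, pre-dose rates of 1% to 10% take the ratio from 3.0 to between 2.33 and 1.31. The risk difference moves only from 4.0 to between 3.96 and 3.6 points. If nobody is positive before dosing, the two counts are identical. Loss of power is not a general consequence: it ranges from large to none across the assumed cases.

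Every rate here is an assumption. Independence between pre-dose and later answers probably overstates the effect, since people positive before dosing are likely to be positive again. The correction is still worth making, because it is cheap and this is the table that compares nonserious C-SSRS findings between arms.

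**What to change.** In SAP 6.13.3.10.2:

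1. State that each C-SSRS item and composite counts yes answers at assessments after the first dose through Visit 801.
2. Show the Visit 1 and Visit 2 answers in a separate baseline column.
3. Add the number of participants whose worst postbaseline category exceeds their worst pre-dose category, in parallel with the PHQ-9 analysis.
4. Keep the all-visit listing as planned.

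Separately, reconcile the Safety Analysis Set in protocol Table GPIA.4 with that in SAP Table GPIA.6.1.

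The cost is SAP wording, one extra column and one extra set of rows. No new data are needed.

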### 6.13.3.11. Malignancy

Treatment-emergent malignancy will be considered an AESI. The counts and percentages of participants with treatment emergent malignancy will be summarized by treatment and PT with decreasing order. Detailed searching criteria can be found in Appendix 1.

### 6.13.3.12. Renal Safety

Laboratory measures related to renal safety will be analyzed as specified for laboratory measurements in Section 6.13.6.

Two shift tables examining renal function will be created. A min-to-min shift table of estimated glomerular filtration rate (eGFR) estimated by the Chronic Kidney Disease Epidemiology Collaboration (CKD-EPI) equation with units ml/min/1.73m^2, using categories ( $<30, \geq 30$  to <45,  $\geq 45$  to  $<60, \geq 60$  to <90, and  $\geq 90$  mL/min/1.73m^2). A max-to-max shift table of urine albumin-to-creatinine ratio (UACR), using the categories UACR <30 mg/g, 30 mg/g  $\leq$  UACR  $\leq 300$  mg/g, UACR >300 mg/g (respectively, these represent normal, microalbuminuria, and macroalbuminuria).

Mixed model repeated measure analyses for eGFR and UACR will be provided. Log transformation will be performed for UACR.

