Injection training with Autoinjector demonstration device ^k		X																

Visit ^a	1	2 ^b	3	4	5	6	7	8	9	10	11	12	13	14	15	99°	ED ^d	801e
Week of Treatment	-2	0	4	8	12	16	20	24	28	32	36	40	44	48	52	52		4 wks Post TxP
Allowable Deviation (days)f		±7	±7	±7	±7	±7	±7	±7	±3	±3	±7	±3	±7	±3	±7	±7		±7
Fasting (>8 hours) Visit ^a	X	X	X	X	X	X	X	X			X		X		X	X	X	X
Telephone Visit									X	X		X		X				
Dispense study drug		X	X	X	X	X	X	X			X		X					
Observe participant administer study drug ⁿ		X																
Participant returns study drugs and injection supplies			X	X	X	X	X	X			X		X		X		X	
Review study participant diary, including study drug compliance			X	X	X	X	X	X	X	X	X	X	X	X	X		X	
						Labo	oratory	Tests										
Serum pregnancy test ^o	X																	
Urine pregnancy test ^p		X			X			X			X		X		X	X	X	
Follicle-stimulating hormone ^q	X																	
Chemistry panel (include Cr for eGFR calculation ^s and glucose)	X	X			X			X			X		X		X		X	X
Lipid panel	X	X						X							X		X	X
Insulin		X			X			X			X		X		X		X	X
C-peptide		X			X			X			X		X		X		X	X
Free fatty acids	X	X						X							X		X	X
Urinary albumin/creatinine ratio	Xr							X							X		X	X
Cystatin-c	Xr							X							X		X	X

Visit ^a	1	2 ^b	3	4	5	6	7	8	9	10	11	12	13	14	15	99°	ED ^d	801e
Week of Treatment	-2	0	4	8	12	16	20	24	28	32	36	40	44	48	52	52		4 wks Post TxP
Allowable Deviation (days)f		±7	±7	±7	±7	±7	±7	±7	±3	±3	±7	±3	±7	±3	±7	±7		±7
Fasting (>8 hours) Visit ^a	X	X	X	X	X	X	X	X			X		X		X	X	X	X
Telephone Visit									X	X		X		X				
Calcitonin	Xr				X			X							X		X	X
Hematology	Xr				X			X							X		X	X
HbA1c	X	X			X			X			X		X		X		X	X
Pancreatic amylase, lipase	X	X			X			X							X		X	X
Thyroid stimulating hormone	Xr																	
Immunogenicity (includes PK sample) ^{t, u}		X	X		X			X			X				X		X	X
Mental Health Questionnaires																		
Patient Heath Questionnaire- 9 (PHQ-9) ^v	X	X			X			X			X		X		X	X	X	X
Columbia-Suicide Severity Rating Scale (C-SSRS) (Baseline/Screening Version) ^v	X																	
Columbia-Suicide Severity Rating Scale (C-SSRS) (Since Last Visit Version) ^v		X	X	X	X	X	X	X	X	X	X	X	X	X	X	X	X	X
Self-Harm Supplement Form ^{v,w}	X	X	X	X	X	X	X	X	X	X	X	X	X	X	X	X	X	X
Self-Harm Follow-up Form ^w	X	X	X	X	X	X	X	X	X	X	X	X	X	X	X	X	X	X
	PROs ^x																	
Short-Form-36 Health Survey (SF-36), version 2, acute form		X													X		X	

Visita	1	2 ^b	3	4	5	6	7	8	9	10	11	12	13	14	15	99°	ED ^d	801e

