- P A urine pregnancy test must be performed for all female participants at Visit 2. The result should be available prior to the first injection of study drug(s) for women of childbearing potential only. Additional pregnancy tests (beyond those required per the Schedule of Activities) should be performed at any time during the trial if a menstrual period is missed, there is clinical suspicion of pregnancy, or as required by local law or regulation. For sites who can't perform urine pregnancy test, a local serum pregnancy test can be performed instead.
- 9 Follicle-stimulating hormone test performed at Visit 1 for postmenopausal women at least 40 years of age with an intact uterus, not on hormone therapy, and who have had spontaneous amenorrhea for at least 12 months without an alternative medical cause.

- ^r Screening visit assessment will be used to confirm eligibility. If calcitonin results are not available, a final review of eligibility will occur at Visit 2 before randomization can proceed.
- s The CKD-EPI equation will be used by the central lab to estimate and report eGFR.
- t In the event of systemic drug hypersensitivity reactions (immediate or non-immediate), additional unscheduled blood and urine samples will be collected as detailed in Appendix 6.
- ^u PK and ADA samples for immunogenicity must be taken prior to drug administration.
- v The C-SSRS, Self-Harm Supplement Form and PHQ-9 should be administered after assessment of adverse events. For this study, the C-SSRS is adapted for the assessment of the ideation and behavior categories only. The Intensity of Ideation and Lethality of Behavior sections are removed. The C-SSRS questionnaire will be completed by investigators, while PHQ-9 will be completed by participants. The Self-Harm Supplement Form is only required if responses to the C-SSRS indicate that the patient needs to be further evaluated for self-harm risk.
- w Self-Harm Follow-up Form is only required if triggered by the Self-Harm Supplement Form, per instructions in the form. Self-Harm forms will be completed by investigators.
- x All PROs should be completed before any other study procedures if the participant is not adversely affected by the fasting condition or completed after the participant has sufficiently recovered from the preceding visit procedures.

3. Introduction

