6.2. Exclusion Criteria

Participants are excluded from the study if any of the following criteria apply:

Medical Conditions

Diabetes-related

- 6. Have type 1 diabetes mellitus (T1DM) or T2DM, history of ketoacidosis, or hyperosmolar state/coma
- 7. Have HbA1c ≥6.5% or fasting serum glucose (FSG) ≥7.0 mmol/L, as determined by the central laboratory at Visit 1

Obesity-related

- 8. Have a self-reported change in body weight >5 kg within 3 months prior to screening
- 9. Have a prior or planned surgical treatment for obesity (excluding liposuction or abdominoplasty if performed >1 year prior to screening)
- 10. Have or plan to have endoscopic and/or device-based therapy for obesity or have had removal within the last 6 months (for example, mucosal ablation, gastric artery embolization, intragastric balloon and duodenal-jejunal endoluminal barrier)

Other medical

- 11. Have renal impairment measured as estimated glomerular filtration rate (eGFR) <30 mL/min/1.73 m², calculated by Chronic Kidney Disease-Epidemiology as determined by central laboratory during screening
- 12. Have a known clinically significant gastric emptying abnormality (for example, severe gastroparesis or gastric outlet obstruction) or chronically take drugs that directly affect GI motility
- 13. Have had a history of chronic or acute pancreatitis
- 14. Have a thyroid stimulating hormone (TSH) <0.4 or >6.0 mIU/L at screening visit

Note: Participants receiving treatment for hypothyroidism may be included, provided their thyroid hormone replacement dose has been stable for at least 3 months.

Note: TSH values above the normal range can, in some participants, suggest subclinical hypothyroidism. If, in the investigator's opinion, the participant has subclinical hypothyroidism and may require initiation of thyroid hormone replacement during the course of the study, the participant should be excluded from the study.

- 15. Have obesity induced by other endocrinologic disorders (for example, Cushing syndrome) or diagnosed monogenetic or syndromic forms of obesity (for example, Melanocortin 4 Receptor deficiency or Prader Willi Syndrome)
- 16. Have a history of significant active or unstable Major Depressive Disorder (MDD) or other severe psychiatric disorder (for example schizophrenia, bipolar disorder, or other serious mood or anxiety disorder) within the last 2 years

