## 6.2. General Considerations

Statistical analysis of this study will be the responsibility of Eli Lilly and Company (Lilly) or its designee. Some analyses and summaries described in this analysis plan may not be conducted if not warranted by data (e.g., few events to justify conducting an analysis). Additional analyses of the data may be conducted as deemed appropriate.

Unless otherwise noted, tests of treatment effects will be conducted at a 2-sided alpha level of 0.05, and the confidence interval (CI) will be calculated at 95% 2-sided.

Unless specified otherwise, efficacy and safety will be assessed using the modified intention-totreat (mITT) population, and data will be analyzed based on the randomized treatment (that is, not the actual treatment received by the participant). For primary efficacy analysis, the efficacy analysis will be conducted using Efficacy Analysis Set (EAS). Safety analysis will be conducted using Safety Analysis Set (SS).

Summary descriptive statistics for continuous measures will include sample size, mean, standard deviation (SD), median, minimum, and maximum. The analysis model to make comparisons among treatment groups relative to continuous measurements assessed over time will be either analysis of covariance (ANCOVA) or a mixed model for repeated measures (MMRM).

Kaplan-Meier method will be used for estimation of cumulative event-free survival rates over time, and Cox proportional hazards regression analysis will be used to compare hazards rates among treatments.

Summary statistics for categorical measures (including categorized continuous measures) will include sample size, frequency, and percentages. Logistic regression will be used to examine the treatment difference in binary efficacy outcomes if there is a need to adjust for covariate. Otherwise, Fisher's exact test will be used to examine the treatment difference.

Summary statistics for discrete count measures will include sample size, mean, SD, median, minimum, and maximum.

Unless specified otherwise, baseline will be defined as the last available non-missing measurement during Visit 1 to Visit 2. For the safety related parameters, the definition of baseline and postbaseline are specified in Table GPIA.6.2.

Analysis Set	Analysis Type	Baseline	Postbaseline
SS	1.1) Treatment-	The baseline period is defined	Starts after the first dose of study
	Emergent Adverse	as the start of screening and	treatment and ends at the end of the

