## 6.13.6. Clinical Laboratory Evaluation

Limits from the performing lab will be used to define low (L) and high (H). Descriptive summaries by treatment and by nominal visit will be provided for the baseline and postbaseline values as well as the change from baseline values. The associated descriptive will be presented in System International (SI) units and in conventional (CN) units.

Observed and change from baseline values for each visit may be displayed in plots for participants who have both a baseline and at least 1 postbaseline planned measurement. Baseline will be the last nonmissing observation prior to taking first study drug. Unplanned measurements will be excluded from plots.

A shift table will be provided including unplanned measurements. The shift table will include the number and percentage of participants within each baseline category (low, normal, high, or missing) versus each postbaseline category (low, normal, high, or missing) by treatment. The proportion of participants shifted will be compared between treatments using Fisher's exact test.

For qualitative laboratory analytes, the number and percentage of participants with normal and abnormal values will be summarized by treatment.

A listing of abnormal findings will be created for laboratory analyte measurements, including qualitative measures. The listing will include participant identification, treatment group, laboratory collection date, study day, analyte name, and analyte finding.

The MMRM model or ANCOVA (if MMRM model is not applicable) will be used for the analysis during the treatment period for the continuous measurements for selected lab tests.

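### Creatinine-based eGFR is the only filtration measure with its own renal analysis; cystatin C is already sampled but not named in the SAP and should support it

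*SAP*

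**What the plan says.** **Source of eGFR.** The laboratory rows of the Schedule of Activities (protocol Section 2) list "Chemistry panel (include Cr for eGFR calculation", and footnote s adds: "The CKD-EPI equation will be used by the central lab to estimate and report eGFR". Neither document gives the version of the equation.

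**Renal analyses.** SAP 6.13.3.12 opens with a general clause: "Laboratory measures related to renal safety will be analyzed as specified for laboratory measurements in Section 6.13.6". It then specifies:
- "A min-to-min shift table of estimated glomerular filtration rate (eGFR) estimated by the Chronic Kidney Disease Epidemiology Collaboration (CKD-EPI) equation", in five categories;
- a max-to-max shift table of UACR in three categories;
- repeated-measures models for eGFR and for log-transformed UACR.

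Subsections 6.13.3.12.1 and 6.13.3.12.2 add acute renal events, which are adverse events of special interest, and dehydration events.

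**Cystatin C.** The Schedule samples it at Visit 1, Week 24, Week 52, ED and Visit 801. Footnote r is attached to the Visit 1 sample: "Screening visit assessment will be used to confirm eligibility". No eligibility criterion uses cystatin C. Criterion 11 uses eGFR, "calculated by Chronic Kidney Disease-Epidemiology as determined by central laboratory during screening", and criterion 24 uses eGFR to set the calcitonin limit. The SAP does not name cystatin C and defines no eGFR based on it.

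**The concern.** Serum creatinine depends on how much creatinine the body produces as well as on how fast the kidney clears it. If production follows muscle mass, and participants on tirzepatide lose more muscle than those on placebo because they lose more weight, creatinine falls more in the active arms with filtration unchanged. Creatinine eGFR then rises in those arms. The error would differ by arm and favour the drug, and neither randomisation nor a repeated-measures model removes it, because it arises after randomisation and as a result of treatment.

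The protocol (Appendix 6.1.12) bases renal safety on repeated tests of renal function together with adverse events. A modest, sustained fall in filtration could therefore be offset in the one filtration measure that is formally compared between arms. A second marker is already being drawn, but the plan does not commit to using it for that comparison.

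**Working it through.** No sample size, power or alpha figure bears on this point, so there is no planned figure to reproduce. The check has two parts.

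**1. What is sampled and what is analysed**

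| Measure | Scheduled visits (each also at ED) | Dedicated analysis in SAP 6.13.3.12 |
|---|---|---|
| Creatinine / eGFR | Visits 1 and 2; Weeks 12, 24, 36, 44, 52; Visit 801 (8) | Shift table and model |
| UACR | Visit 1; Weeks 24, 52; Visit 801 (4) | Shift table and model (log scale) |
| Cystatin C | Visit 1; Weeks 24, 52; Visit 801 (4) | None |

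Counting the subsections, six renal analyses are named: eGFR shift, UACR shift, eGFR model, UACR model, acute renal events and dehydration events. Two use eGFR, four do not, and none names cystatin C. UACR has the same sampling visits as cystatin C and still receives both a shift table and a model, so the sparse schedule does not rule these analyses out.

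The screening value can serve as baseline, since in SAP 6.2 "baseline will be defined as the last available non-missing measurement during Visit 1 to Visit 2", and Table GPIA.6.2 uses the same Visit 1 to Visit 2 window for laboratory measures.

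**2. Illustrative size of the drift**

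From the documents: a difference of at least 11 points in percent weight change versus placebo, which is the sample-size assumption (protocol 10.1; SAP 5.1).

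Assumed, and not in the documents: an upper weight loss of 15%; 20% to 40% of the loss is lean tissue; lean mass is 58% of body weight; creatinine production falls in proportion to lean mass; eGFR is proportional to creatinine raised to −e, with e = 0.329, 0.411 or 1.209; eGFR is 95 mL/min/1.73 m² at baseline.

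Fractional lean loss f = weight loss × lean share / 0.58:
- low: 0.11 × 0.20 / 0.58 = 0.038
- high: 0.15 × 0.40 / 0.58 = 0.103

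This is about 4% to 10%. With filtration constant, the apparent rise in eGFR is (1 − f)^(−e) − 1:

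| f | e = 0.329 | e = 0.411 | e = 1.209 |
|---|---|---|---|
| 0.04 | 1.4% | 1.7% | 5.1% |
| 0.10 | 3.5% | 4.4% | 13.6% |

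With f unrounded, the extremes are 1.3% and 14.1%. At 95 mL/min/1.73 m² the tabulated extremes are 0.014 × 95 = 1.3 and 0.136 × 95 = 12.9, or about +1 to +13.

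The same assumptions show how large a decline could be hidden. If true filtration falls by a fraction d, steady-state creatinine changes by the factor (1 − f)/(1 − d), and eGFR by [(1 − d)/(1 − f)]^e. This equals 1 when d = f, whatever the exponent. A sustained fall of 4% to 10% (3.8 to 9.5 mL/min/1.73 m² at 95) could thus appear as no change.

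**The case against.** **The renal plan is broader than eGFR.** A reader might infer that renal safety rests on creatinine eGFR alone. The documents do not support that, because four of the six named renal analyses do not use eGFR. These four do not close the filtration gap, however. UACR reflects albumin leakage and has creatinine in its own denominator. Acute renal and dehydration events are reported terms and do not measure filtration.

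**Cystatin C is not left out altogether.** It is a listed central laboratory test (protocol Appendix 2), and the opening clause of 6.13.3.12 sends renal laboratory measures to 6.13.6, where "Descriptive summaries by treatment and by nominal visit will be provided for the baseline and postbaseline values as well as the change from baseline values". Section 6.13.6 also provides a low/normal/high shift table with Fisher's exact test, and a model for selected tests. It would therefore be wrong to say that cystatin C has no place in the SAP. What remains is that 6.13.6 gives no filtration categories, does not say which tests are selected for modelling, and does not place cystatin C beside eGFR.

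**The remedy does not address acute injury.** This objection stands. The highest dose is reached at Week 20, and the only scheduled on-treatment cystatin C samples are at Weeks 24 and 52. They cannot show a brief decline during escalation. Nor does creatinine drift change which reported terms the renal-event search counts. A reading that acute renal events would be hidden is not supported.

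**The mechanism is external.** This also stands. Neither document discusses muscle loss, and the computed range spans about tenfold. Bias is a conditional possibility here, and the documents do not establish it.

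**Cystatin C may vary with body fat,** in a trial designed to reduce body fat. This is a reason to report both versions and not to replace one with the other.

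**Conclusion.** The point holds as a gap in specifying a safety analysis, and it is minor. Creatinine-based eGFR is the only filtration measure given a dedicated shift table and model. Cystatin C is collected at baseline, twice on treatment, at ED and at follow-up, with no stated analytic purpose. The one purpose the Schedule attaches to it, eligibility, matches no criterion.

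If lean mass is lost mainly on active drug, creatinine eGFR would be raised there by about 1% to 14% with filtration unchanged, and a modest sustained decline could be masked. The direction follows from the mechanism. The size depends on the assumed weight loss, lean share, lean fraction and exponents, and should be read as a range and not an estimate. Sample size, alpha and the primary analysis are unaffected.

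**What to change.** In SAP 6.13.3.12, name cystatin C and add eGFR based on cystatin C, and on creatinine and cystatin C combined, as supportive analyses. Use the same five-category shift table and the same type of repeated-measures model, at the visits where cystatin C is collected, with the Visit 1 value as baseline. Show the results beside the creatinine version and state which equations are used. Both markers are drawn at all of these visits, so the combined version needs no further samples.

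One detail matters for the comparison. Apart from ED, creatinine has six scheduled post-baseline values and cystatin C has three, and a minimum over more values tends to be lower. The creatinine shift table placed alongside should therefore be restricted to the shared visits.

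The cost is two extra tables, a shift table and a model table, each carrying both equations, and no new visits or samples. The limits should be stated with the results: two scheduled on-treatment time points, no information on transient declines during escalation, and possible dependence of cystatin C on body fat. Specifying this before unblinding avoids choosing a filtration marker after the results are known.
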